3.2. Study Design Rationale

Rationale for Single Agent Talacotuzumab Monotherapy in Part A

Studies with CSL362 identified 9 mg/kg as the RP2D. Talacotuzumab is produced in a different cell line with a different process compared with the Phase 1 study (CSLCT-AML-11-73) CSL362 drug product. To confirm the safety and RP2D of talacotuzumab, a safety run-in period of talacotuzumab at 9 mg/kg will be evaluated first as monotherapy in Part A of this study.

Rationale for DACOGEN

Decitabine is an appropriate comparator in this study as it is approved for the treatment of this AML population in the European Union (EU) and 21 other countries (as of November 2014) and is a treatment option recommended in treatment guidelines such as the National Comprehensive Cancer Network.^{9,28}

The proposed schedule of decitabine administered at a dose of 20 mg/m² body surface area by IV infusion over 1 hour repeated daily for 5 consecutive days (ie, 5 doses per treatment cycle) is outlined in more detail in the prescribing information. The total daily dose of decitabine must not exceed 20 mg/m² and the total dose per treatment cycle must not exceed 100 mg/m².

Rationale for Dose of Talacotuzumab

Safety: The talacotuzumab dose and schedule for this study was planned using CSL362 results from a Phase 1 study (CSLCT-AML-11-73). CSL362 has been deemed safe and well tolerated as no AE ≥ CTCAE Grade 3 has occurred in 9 subjects dosed at 9 mg/kg every 14 days in the CSL-sponsored Phase 1 study. Despite the initially observed adverse event of severe (CTCAE Grade 3) infusion-related reaction at low doses, no subject at the 9-mg/kg dose level experienced a severe infusion related reaction after the institution of mandatory pre-medication and a prolonged infusion time to 3 hours.

Pharmacokinetics: With CSL362, the 9 mg/kg dose exhibits predictable PK above the nonlinear pharmacokinetic range where higher clearance and shorter half-life was observed at lower doses. Additionally, the half-life of 4 to 5 days supports the every 14-day dosing frequency. At 9 mg/kg, the trough concentration of CSL362 from the majority of subjects is expected to exceed the estimated concentration needed to saturate the CD123 target as measured by the peripheral marker monocytes. This dose is selected to ensure sustained target saturation throughout the dosing period, particularly considering that 1 of the therapeutic targets is anticipated to be the leukemic stem cell niche in the bone marrow.

Pharmacodynamics: For CSL362, the pharmacodynamic pattern and kinetics of biomarkers, including basophils, pDC cells, NK cells, monocytes, etc. are generally comparable regardless of the cycle number. Aside from CD123 expressing cell types, CSL362 at 9 mg/kg does not seem to significantly affect other cells, or only affect transiently with return to baseline expected within 3 days, as in the case of NK cells. In summary, 9 mg/kg every 2 weeks is a safe dose within the linear PK dose range that is expected to provide adequate exposure and sustained target saturation throughout the dosing interval for both peripheral and bone marrow blasts and LSCs.

Rationale for Talacotuzumab Dose in Combination with DACOGEN

Decitabine has a safety profile that allows for its use as an outpatient therapy for elderly and physically impaired patients with AML.²⁵ Treatment with decitabine is associated with myelosuppression and adverse events related to myelosuppression (ie, thrombocytopenia, anemia, neutropenia, and febrile neutropenia) which are however common in both treated and untreated patients with AML.¹⁵ Decitabine administered at the recommended dose (20 mg/m²) and schedule (Days 1 to 5) currently is being tested in combination with a variety of experimental compounds.^{25,26} The safety and PK data obtained for CSL362 in the ongoing Phase 1 study support the proposed combination regimen with decitabine using full doses of both agents. The safety profiles of both agents are considerably different. While treatment with decitabine may exacerbate the myelosuppression frequently observed in patients with AML, no impact on normal hematopoiesis was observed in AML patients in CR exposed to increasing doses of CSL362. This Phase 1 safety observation supports the scientific hypothesis that CD123 is differentially expressed on normal hematopoietic stem cells and LSCs. Therefore, by specifically targeting the LSCs and the emerging leukemic blast cells, the addition of talacotuzumab may not lead to an aggravation of the myelosuppression or extension of the time of hematopoietic recovery observed in AML patients receiving decitabine. Lastly, pharmacokinetic drug-drug interaction between decitabine and talacotuzumab is not expected given the different absorption, distribution, metabolism, and excretion (ADME) properties and metabolic pathways utilized by these agents.

Rationale for Randomization

In Part B, subjects will be randomized to receive either decitabine + talacotuzumab (Arm 1) or decitabine alone (Arm 2). Randomization will minimize bias in the assignment of subjects to treatment groups, to increase the likelihood that known and unknown subject attributes (eg, demographic and baseline characteristics) are evenly balanced across treatment groups, and to enhance the validity of statistical comparisons across treatment groups. Additionally, enrollment into the treatment arms is stratified by baseline ECOG performance status score (0-1 versus 2) and type of AML (de novo versus secondary), prognostic factors known to affect clinical outcomes.⁹

After Interim Analysis #2, enrollment to the study was closed. Subjects receiving talacotuzumab + decitabine (Arm 1) stopped talacotuzumab treatment and were allowed to continue to receive decitabine alone, according to Principal Investigator decision and subject agreement. This was based on an IDMC review that noted a lack of efficacy advantage of talacotuzumab + decitabine versus decitabine alone, the incidence of infusion-related reactions, and the complexities with premedications for drug administration that made the benefit/ risk ratio not favorable to continue treatment with talacotuzumab.

Rationale for Primary Endpoints

For this Phase 2/3 study, CR rate and OS are chosen as the 2 primary endpoints for the reason that a higher CR rate would be an early and clinically meaningful measure of efficacy and an improvement in OS would demonstrate the broadest and most meaningful measure of treatment benefit.³²

Rationale for Biomarker Evaluation

Biomarker samples will be collected to evaluate the mechanism of action of the combination of decitabine + talacotuzumab, to establish the threshold of CD123 expression needed for clinical response, and to help explain inter-individual variability in clinical outcomes or to identify population subgroups that respond differently to decitabine + talacotuzumab or decitabine alone.

Rationale for Pharmacodynamic Marker Evaluation

Previous CSL362 pre-clinical and clinical studies in subjects with AML demonstrated that CD123-positive pDC and basophils are reliable cellular pharmacodynamic markers for CSL362 activity.^{3,33} These cells were completely depleted within hours of CSL362 infusion and depletion was sustained for ≥ 15 days at doses ≥ 3.0 mg/kg. Natural killer cells are critical to the mechanism of action of talacotuzumab (CSL362) and quantification may reveal an association with clinical response. Natural killer cell counts are reduced in the first few hours after dosing but stabilized at Day 3 and thereafter, indicating that this fluctuation may be caused by NK cell redistribution.³³

Rationale for Assessment of CD123 Expression

CD123 is expressed in AML blasts and LSCs in a large percentage of AML patients (75-89%).^{14,17,27} The percentage of CD123+ leukemic blasts at diagnosis has been correlated with a poor response to intensive chemotherapy.³⁶ In a study by Ehninger,¹⁰ 78% of newly diagnosed AML patients had AML blasts that were positive for CD123 expression. The cutoff for positive flow measurements in this study was set to >10 , based on the geometric mean fluorescence intensities (MFIs) of CD123 in blasts in relation to the MFIs of lymphocytes (considered negative for CD123).¹⁰

Rationale for Minimal Residual Disease Assessment

Assessment of minimal residual disease (MRD) is becoming an important evaluation to determine the depth of response beyond clinical CR in AML and other hematologic malignancies,¹³ and it has been shown that MRD assessment adds prognostic value beyond both karyotype and specific gene mutations.^{2,18}

Rationale for Immunophenotyping

The activity of talacotuzumab depends on its ability to engage its target (CD123) and recruit effector cells of the immune system for cell killing. Therefore, the ultimate activity of this agent depends not only on expression of the target by AML blasts and LSCs, but also on the fitness of the host immune system. Therefore, we will determine the state of the host's immune system. In addition, the biomarker plan will attempt to address the effect of decitabine on the host immune system, with particular attention to NK effector cell number and function.

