Although the exact phenotypes of CD34+/CD38- AML stem cells remain controversial, the constitutive over-expression of the CD123 antigen is common.¹¹ CD123 over-expression on LSCs is conserved on the emerging leukemic blast cells and constitutes a marker of poor clinical prognosis because of the association with (i) known adverse immune-phenotypes such as FLT3 internal tandem duplication (FLT3-ITD), (ii) a lower rate of complete responses following conventional chemotherapy and (iii) shorter disease-free survival and overall survival (OS).^{10,34,36} Levels of CD123 in normal hematopoietic stem cells and early hematopoietic progenitor cells are considerably lower than the overexpression found on LSCs and blasts in AML.^{10,17} Results from the ongoing Phase 1 study of CSL362 suggest that targeting CD123-overexpressing LSC and leukemic blast cells with an anti-CD123 antibody may not affect normal hematopoiesis.

The safety assessments and confirmation of the RP2D in Part A of this study have been designed to supplement the biophysical and preclinical toxicology comparability testing of the anti-CD123 monoclonal antibody produced in different Chinese hamster ovary cell lines; CSL362 was produced in the CHO-S cell line and used for the Phase 1 study while talacotuzumab was produced in GS-CHOK1SV cells and will be used for all subsequent clinical studies. Results from preclinical testing are provided in Section 1.1 and the talacotuzumab (JNJ-56022473) Investigator's Brochure.¹⁶

The scientific rationale for the seamless Phase 2/3 portion of this study (Part B) is that the combination of decitabine and talacotuzumab may have a complimentary/synergistic effect on the leukemic cells.

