2. OBJECTIVES, ENDPOINTS, AND HYPOTHESIS

2.1. Objectives and Endpoints

2.1.1. Objectives

Primary Objectives

Part A: to assess the safety of talacotuzumab monotherapy and confirm the RP2D in subjects with AML for whom experimental therapy is appropriate (as assessed by their treating physician).

Part B: The primary objectives of the study are to assess CR rate and OS in subjects with previously untreated AML who are not eligible for intense induction chemotherapy and who are randomly assigned to receive decitabine plus talacotuzumab at the RP2D or decitabine alone.

Secondary Objectives (Part B)

The secondary objectives are:

- To assess EFS;
- To determine the overall response rate (ORR) defined as rate of complete response (CR) and complete response with incomplete blood count recovery (CRi);
- To determine the rate of CR plus MRD negative CRi
- To assess the relapse-free survival (RFS);
- To assess time to response and duration of response for subjects who achieve CR/CRi;
- To assess minimal residual disease (MRD);
- To assess the safety profile of talacotuzumab in combination with decitabine;
- To assess the pharmacokinetics of talacotuzumab and decitabine alone and in combination;
- To assess the immunogenicity talacotuzumab alone (Part A) and in combination with decitabine (Part B);
- To assess patient-reported outcomes (PROs) using the FACT-Leu and EQ-5D-5L.

Exploratory Objectives

The exploratory objectives are:

- To explore PK/PD relationships of talacotuzumab through analysis of talacotuzumab PK, biomarkers, PD markers, and clinical end points;
- To explore biomarkers predictive of clinical response;
- To collect medical resource utilization (MRU) data that may be used in future economic modeling (the construction and reporting of the economic model will be conducted separately from this study).

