11.4. Efficacy Analyses

Kaplan-Meier estimates of time to events, including OS and EFS will be presented, along with a stratified (by baseline ECOG performance status and type of AML) log-rank test comparing the 2 treatment arms. Median OS along with corresponding 95% confidence intervals (CIs) will be obtained from the Kaplan-Meier estimates. Cox's regression (stratified by baseline ECOG performance status and type of AML) will be applied to obtain the hazard ratio estimate and the corresponding 95% CI. Additional Cox's regression may be performed to include appropriate baseline prognostic variables.

Number and percent of subjects who have CR, CR+CRi, and CR plus MRD negative CRi will be calculated and compared between the 2 treatment arms using Fisher's exact test. Time to response and duration of response will also be summarized for subjects who have CR, CR+CRi, and CR plus MRD negative CRi.

Descriptive analysis will be performed for RFS.

Statistical analyses will be performed for all randomized subjects, as well as for subgroups defined by important baseline or disease characteristics, including CD123 status. Additional efficacy analyses may be performed to include appropriate data from Part A.

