11.8. Biomarker Analyses

Biomarker studies are designed to identify markers predictive of response (or resistance) to talacotuzumab. Analyses will be stratified by clinical covariates or molecular subgroups using the appropriate statistical methods (eg, parametric or non-parametric, univariate or multivariate, analysis of variance [ANOVA], or survival analysis, depending on the endpoint). Correlation of baseline expression levels or changes in expression levels with clinical parameters will identify responsive (or resistant) subgroups in addition to immune cells, genes and pathways attenuated following treatment with talacotuzumab.

Basophils and pDCs, as potential pharmacodynamic measures, will be listed, tabulated, and where appropriate, plotted. Subjects may be grouped by cohort, dose, or clinical response. Data from CD123 expression will be used as prognostic factors for clinical outcomes to explore if potential thresholds can be established for future subject selection. Results of biomarker and pharmacodynamic analyses may be presented in a separate report. Planned analyses are based on the availability of clinically valid assays and may be deferred if emerging study data show no likelihood of providing useful scientific information.

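### Protocol 11.8 seeks markers predictive of talacotuzumab response but names only a prognostic CD123 analysis as the route to a selection threshold (minor, exploratory).

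*Protocol*

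**What the plan says.** **Aim.** Protocol 3.2 (Rationale for Biomarker Evaluation) wants samples "to establish the threshold of CD123 expression needed for clinical response" and to "identify population subgroups that respond differently to decitabine + talacotuzumab or decitabine alone". The exploratory objectives in 2.1.1 include "To explore biomarkers predictive of clinical response". Section 11.8 opens with "Biomarker studies are designed to identify markers predictive of response (or resistance) to talacotuzumab".

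**Method.** Section 11.8 then says of CD123: "Data from CD123 expression will be used as prognostic factors for clinical outcomes to explore if potential thresholds can be established for future subject selection". It also plans to correlate baseline expression, or its change, with clinical parameters. It allows stratification by covariates or molecular subgroups, with methods chosen to suit the endpoint. Treatment arm, the decitabine-alone comparison and a treatment-by-marker interaction are not mentioned there.

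**Prognosis.** Protocol 1.4 says CD123 over-expression "constitutes a marker of poor clinical prognosis", citing fewer complete responses after conventional chemotherapy and shorter survival. Protocol 3.2 adds that the percentage of CD123-positive blasts at diagnosis "has been correlated with a poor response to intensive chemotherapy".

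**Related provision.** Protocol 11.4 plans efficacy analyses for all randomised subjects and for "subgroups defined by important baseline or disease characteristics, including CD123 status". SAP 5.13 lists nine subgroup factors, and CD123 is not among them. The supplied SAP contains no CD123 analysis.

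**The concern.** A threshold for choosing future patients is a predictive quantity: the CD123 level above which adding talacotuzumab improves outcome. A prognostic analysis answers a different question, namely whether outcome differs by CD123 level. The two agree only if CD123 has no bearing on outcome without the antibody, and the protocol's own background makes that doubtful.

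If high CD123 does worse on decitabine, a benefit confined to high-CD123 patients can be cancelled by their poorer prognosis. If the antibody does nothing, the association can still suggest a cutoff, and it would favour low-CD123 patients for an anti-CD123 drug. Randomisation separates the two effects, because the control arm shows the prognostic gap directly. Section 11.8 does not say that it will be used for the threshold.

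**Working it through.** The documents state no sample size, power, cutoff or interaction effect for CD123, so there is no CD123 figure to reproduce. The check is algebraic, followed by illustrations under stated assumptions.

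**1. What the association estimates.** Let control CR be c_H in high and c_L in low CD123, and let the drug add b_H and b_L. With 1:1 allocation:
- high minus low within Arm 1 = (c_H − c_L) + (b_H − b_L)
- high minus low, arms pooled = (c_H − c_L) + (b_H − b_L)/2
- interaction (arm difference in high minus arm difference in low) = b_H − b_L

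Only the third is free of the prognostic gap c_H − c_L.

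**2. Inputs.** CD123-positive 78% (a study cited in Protocol 3.2). Overall control CR 15% (Protocol Table 9). Assumed control CR is 13% in positives and 22% in negatives, which averages 0.78 × 13 + 0.22 × 22 = 14.98%.

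**3. A real benefit hidden.** Let the drug add 10 points in positives only.
- Arm 1: 23% vs 22%, a contrast of +1 point
- Pooled: (13 + 23)/2 = 18% vs 22%, a contrast of −4 points
- Interaction: +10 points

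With 50% CD123-high and control CR 10% vs 20%, the same benefit gives an Arm 1 contrast of 0 (20% vs 20%) and a pooled contrast of −5 (15% vs 20%). With no prognostic gap the Arm 1 contrast is +10, which is correct.

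The same holds for OS. An assumed prognostic HR of 1.5 and a drug HR of 0.7 in high CD123 only give an Arm 1 high-versus-low HR of 1.5 × 0.7 = 1.05.

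**4. A signal with no drug effect.** This is the probability that a pooled two-proportion z-test of CR by CD123 is significant at two-sided 0.05, by exact enumeration with a 78/22 split:

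| Positive vs negative CR | N = 160 | N = 400 |
|---|---|---|
| 15% vs 15% (no gap) | 5% | 5% |
| 14% vs 19% | 13% | 23% |
| 13% vs 22% | 28% | 54% |
| 12% vs 27% | 57% | 91% |

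In the rows with a gap, nearly all significant results favour low CD123. At N = 400 the opposite direction has probability 0.001 or less.

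**5. Power of the interaction for OS.** With D deaths and a fraction f of them in high CD123, the variance of the log ratio of hazard ratios is 4/(Df) + 4/(D(1 − f)). For D = 270 and f = 0.78 the standard error is 0.294. Power at two-sided 0.05 is Φ(|ln r|/SE − 1.96):

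| Ratio of HRs, r | f = 0.78 | f = 0.50 |
|---|---|---|
| 0.5 | 66% | 81% |
| 0.6 | 41% | 56% |
| 0.7 | 23% | 31% |

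At 150 deaths with f = 0.78 the range is 15% to 42%. For r = 0.6, 80% power needs about 702 deaths at f = 0.78, or 482 at f = 0.50.

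**The case against.** The strongest reply is Protocol 11.4. The methods there compare the arms (stratified log-rank, Cox, Fisher's exact test) and are extended to subgroups by CD123 status. So the randomised contrast within CD123 groups is in the protocol, and a reader who infers that CD123 is analysed only as a prognostic factor goes too far. This stands, and it narrows the point. It does not remove it: 11.4 gives no cutoff and no interaction, the SAP list drops CD123, and 11.8 does not link the threshold to that comparison.

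A reader might also infer that the association will be run pooled or within Arm 1. Section 11.8 specifies neither. Its wording permits multivariable and survival methods, and the aim in 3.2 is a two-arm question. The biomarker plan mentioned in 3.2 was not supplied and may hold more detail.

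The prognostic evidence concerns conventional and intensive chemotherapy, whereas Part B subjects receive decitabine. No CD123-by-outcome data under decitabine are given, and the gap could be zero. The 78% figure uses a fluorescence-intensity cutoff, while the poor-response statement in 3.2 concerns the percentage of positive blasts. This also stands, so the rates above are illustrations only. In addition, no 0.05 test of CD123 is planned, and a significant association is not itself a derived threshold.

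Finally, the work is exploratory, and Protocol 9.5 makes biomarker assessments discretionary after early termination or poor efficacy. Enrolment closed and talacotuzumab stopped after Interim Analysis #2, so N = 400 is the planned size only. These facts limit the consequence.

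**Conclusion.** The point holds as a minor, exploratory one. Section 11.8 states a predictive aim and names a prognostic analysis as the route to a CD123 selection threshold. If the poor prognosis of high CD123 carries over to decitabine, an association that does not use the arm contrast can hide a benefit or point to the wrong subgroup. Under the assumed 13% vs 22% gap and no drug effect, a pooled test gives a spurious signal in 28% of trials of 160 and 54% of trials of 400. With no gap the rate is 5%.

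A reader might infer that the plan will select the wrong patients. The documents do not support that: the gap under decitabine is unknown, 11.4 offers a partial safeguard, nobody in this trial is selected on CD123, and the CR and OS inference is untouched.

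**What to change.** In Protocol 11.8 and the biomarker plan, base any CD123 threshold on the randomised arm difference across baseline CD123:
- Fit a treatment-by-CD123 interaction with CD123 continuous and report it with its confidence interval. Use logistic regression for CR and stratified Cox for OS.
- Plot the arm difference against CD123, and look for a cutoff only on that curve.
- Align this with the CD123 subgroup analysis in 11.4, and carry it into SAP 5.13 or cross-refer to the document that holds it.
- Report single-arm or pooled associations as prognostic only.
- Label any threshold as hypothesis-generating.

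The cost is analysis wording and work. Screening marrow and matching blood for CD123 are scheduled in Part B without restriction by arm (Time and Events Table 1B). The downside is precision. Interaction power is about 23% to 66% at 270 deaths with 78% CD123-high, for ratios of hazard ratios of 0.7 to 0.5. It is lower if data collection ends at the six-month limit with fewer deaths. A reliable cutoff is unlikely, and the report should say so.
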